# 5.2.5 General Concomitant Medication and Supportive Care Guidelines

Medications or vaccinations specifically prohibited in the exclusion criteria are not allowed during the ongoing trial. If there is a clinical indication for one of these or other medications or vaccinations specifically prohibited during the trial, discontinuation from trial therapy or vaccination may be required. The investigator should discuss any questions regarding this with the Principal Investigator. The final decision on any supportive therapy or vaccination rests with the investigator and/or the subject's primary physician.

#### Acceptable Concomitant Medications

All treatments that the investigator considers necessary for a subject's welfare may be administered at the discretion of the investigator in keeping with the community standards of medical care. All concomitant medication will be recorded on the case report form (CRF) including all prescription, over-the-counter (OTC), herbal supplements, and IV medications and fluids. If changes occur during the trial period, documentation of drug dosage, frequency, route, and date may also be included on the CRF.

All concomitant medications received within 28 days before the first dose of trial treatment and 30 days after the last dose of trial treatment should be recorded.

#### **Prohibited Concomitant Medications**

Subjects are prohibited from receiving the following therapies during the Screening and Treatment Phase (including retreatment for post-complete response relapse) of this trial:

- Antineoplastic systemic chemotherapy or biological therapy
- Immunotherapy not specified in this protocol
- Investigational agents other than OBP-301
- Live vaccines within 30 days prior to the first dose of trial treatment and while participating in the trial. Examples of live vaccines include, but are not limited to, the following: measles, mumps, rubella, varicella/zoster, yellow fever, rabies, BCG, and typhoid vaccine.
- Systemic glucocorticoids for any purpose other than to modulate symptoms from an event of clinical interest of suspected immunologic etiology. The use of physiologic doses of corticosteroids may be approved after consultation with the Sponsor.

Subjects who, in the assessment by the investigator, require the use of any of the aforementioned treatments for clinical management should be removed from the trial. Subjects may receive other medications that the investigator deems to be medically necessary.

The Exclusion Criteria describe other medications which are prohibited in this trial.

There are no prohibited therapies during the Post-Treatment Follow-up Phase.

#### 5.2.6 Rescue Medications & Supportive Care

Subjects should receive appropriate supportive care measures as deemed necessary by the treating investigator. Suggested supportive care measures for the management of adverse events with potential immunologic etiology are outlined below and in greater detail in the ECI guidance document. Where appropriate, these guidelines include the use of oral or intravenous treatment with corticosteroids as well as additional anti-inflammatory agents if symptoms do not improve with administration of corticosteroids. Note that several courses of steroid tapering may be necessary as symptoms may worsen when the steroid dose is decreased. For each disorder, attempts should be made to rule out other causes such as metastatic disease or bacterial or viral infection, which might require additional supportive care. The treatment guidelines are intended to be applied when the investigator determines the events to be related to pembrolizumab.

Note: if after the evaluation, the event is determined not to be related, the investigator is instructed to follow the ECI reporting guidance but does not need to follow the treatment guidance (as outlined in the ECI guidance document). Refer to Section 5.2.1 for dose modification.

It may be necessary to perform conditional procedures such as bronchoscopy, endoscopy, or skin photography as part of evaluation of the event. Suggested conditional procedures, as appropriate, can be found in the ECI guidance document.

#### • Pneumonitis:

- For **Grade 2 events**, treat with systemic corticosteroids. When symptoms improve to Grade 1 or less, steroid taper should be started and continued over no less than 4 weeks.
- For **Grade 3-4 events**, immediately treat with intravenous steroids. Administer additional anti-inflammatory measures, as needed.
- Add prophylactic antibiotics for opportunistic infections in the case of prolonged steroid administration.

#### • Diarrhea/Colitis:

Subjects should be carefully monitored for signs and symptoms of enterocolitis (such as diarrhea, abdominal pain, blood or mucus in stool, with or without fever) and of bowel perforation (such as peritoneal signs and ileus).

- All subjects who experience diarrhea/colitis should be advised to drink liberal quantities of clear fluids. If sufficient oral fluid intake is not feasible, fluid and electrolytes should be substituted via IV infusion. For Grade 2 or higher diarrhea, consider GI consultation and endoscopy to confirm or rule out colitis.
- For Grade 2 diarrhea/colitis that persists greater than 3 days, administer oral corticosteroids.
- For **Grade 3 or 4 diarrhea/colitis** that persists > 1 week, treat with intravenous steroids followed by high dose oral steroids.
- When symptoms improve to Grade 1 or less, steroid taper should be started and continued over no less than 4 weeks.
- Type 1 diabetes mellitus (if new onset, including diabetic ketoacidosis [DKA]) or ≥ Grade 3 Hyperglycemia, if associated with ketosis (ketonuria) or metabolic acidosis (DKA)

- For **T1DM** or **Grade 3-4** Hyperglycemia
  - Insulin replacement therapy is recommended for Type I diabetes mellitus and for Grade 3-4 hyperglycemia associated with metabolic acidosis or ketonuria.
  - Evaluate patients with serum glucose and a metabolic panel, urine ketones, glycosylated hemoglobin, and C-peptide.

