# • Hypophysitis:

- For Grade 2 events, treat with corticosteroids. When symptoms improve to Grade 1 or less, steroid taper should be started and continued over no less than 4 weeks. Replacement of appropriate hormones may be required as the steroid dose is tapered.
- For **Grade 3-4** events, treat with an initial dose of IV corticosteroids followed by oral corticosteroids. When symptoms improve to Grade 1 or less, steroid taper should be started and continued over no less than 4 weeks. Replacement of appropriate hormones may be required as the steroid dose is tapered.

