#### • Hyperthyroidism or Hypothyroidism:

Thyroid disorders can occur at any time during treatment. Monitor patients for changes in thyroid function (at the start of treatment, periodically during treatment, and as indicated based on clinical evaluation) and for clinical signs and symptoms of thyroid disorders.

- Grade 2 hyperthyroidism events (and Grade 2-4 hypothyroidism):
  - In hyperthyroidism, non-selective beta-blockers (e.g. propranolol) are suggested as initial therapy.
  - In hypothyroidism, thyroid hormone replacement therapy, with levothyroxine or liothyroinine, is indicated per standard of care.
- Grade 3-4 hyperthyroidism
  - Treat with an initial dose of IV corticosteroid followed by oral corticosteroids. When symptoms improve to Grade 1 or less, steroid taper should be started and continued over no less than 4 weeks. Replacement of appropriate hormones may be required as the steroid dose is tapered.
- Hepatic:
  - For **Grade 2** events, monitor liver function tests more frequently until returned to baseline values (consider weekly).
    - Treat with IV or oral corticosteroids
  - For Grade 3-4 events, treat with intravenous corticosteroids for 24 to 48 hours.
  - When symptoms improve to Grade 1 or less, a steroid taper should be started and continued over no less than 4 weeks.

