#### • Renal Failure or Nephritis:

- For Grade 2 events, treat with corticosteroids.
- For Grade 3-4 events, treat with systemic corticosteroids.
- When symptoms improve to Grade 1 or less, steroid taper should be started and continued over no less than 4 weeks.
- **Management of Infusion Reactions**: Signs and symptoms usually develop during or shortly after drug infusion and generally resolve completely within 24 hours of completion of infusion.

Table 3 below shows treatment guidelines for subjects who experience an infusion reaction associated with administration of pembrolizumab.

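### The steroid prompt for pembrolizumab-related colitis runs backwards by severity: more than 3 days at Grade 2, more than 1 week at Grade 3-4

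*Combined protocol and SAP*

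**What the plan says.** Section 5.2.6 (Rescue Medications & Supportive Care) lists management measures by toxicity. Under Diarrhea/Colitis, two neighbouring lines set the steroid triggers:

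- Grade 2: "For Grade 2 diarrhea/colitis that persists greater than 3 days, administer oral corticosteroids".
- Grade 3 or 4, for an event "that persists > 1 week, treat with intravenous steroids followed by high dose oral steroids".

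The introduction to 5.2.6 presents these measures as suggestions, subject to the treating investigator's judgement, and refers to a separate ECI guidance document for more detail. It also limits their scope: "The treatment guidelines are intended to be applied when the investigator determines the events to be related to pembrolizumab".

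Table 2 in Section 5.2.4 deals separately with pembrolizumab itself. For diarrhea/colitis it is held at Grade 2-3 and permanently stopped at Grade 4.

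**The concern.** A steroid trigger would be expected to come no later as severity rises. Here the Grade 3-4 line waits longer than the Grade 2 line. Section 7.1.2 equates Grade 4 with a life-threatening event, and the colitis entry itself asks staff to watch for bowel perforation. Read literally, the text prompts steroids for life-threatening colitis only after more than a week.

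The event is a foreseen one: the stopping rule in Section 8.7.9 names diarrhea/colitis among the immune-related events that count at Grade 3 or worse. At stake is the timing of treatment at a site that follows the lines as written. The statistical design is not involved.

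**Working it through.** The plan states no figure to reproduce. The check compares the two triggers with each other, and then with the other Grade 3-4 entries in the same section.

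**Step 1: the two colitis triggers (5.2.6, Diarrhea/Colitis).** Grade 2 is prompted after more than 3 days. Grade 3-4 is prompted after more than 1 week, that is, more than 7 days. The thresholds differ by 7 − 3 = 4 days, with the longer wait at the higher grade.

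**Step 2: the other Grade 3-4 steroid entries in 5.2.6.**

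| Toxicity | Grade 3-4 steroid instruction | Waiting period |
|---|---|---|
| Pneumonitis | "immediately treat with intravenous steroids" | None, explicitly immediate |
| Diarrhea/colitis | IV, then high-dose oral | More than 1 week |
| Hypophysitis | "treat with an initial dose of IV corticosteroids followed by oral corticosteroids" | None stated |
| Hyperthyroidism | Initial IV dose, then oral | None stated |
| Hepatic | "For Grade 3-4 events, treat with intravenous corticosteroids for 24 to 48 hours" | None stated |
| Renal failure or nephritis | "For Grade 3-4 events, treat with systemic corticosteroids" | None stated |

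Of six entries, five have no waiting period and one does.

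**Step 3: the delay per event.** Take an event lasting *d* days at constant grade.

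- Days without a steroid prompt under the Grade 3-4 line: min(*d*, 7).
- Days without a prompt if the Grade 2 wait applied: min(*d*, 3).
- Gap: min(*d*, 7) − min(*d*, 3).

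| *d* (days) | Grade 3-4 line as written | Grade 2 wait | Gap |
|---|---|---|---|
| 3 | 3 | 3 | 0 |
| 5 | 5 | 3 | 2 |
| 7 | 7 | 3 | 4 |
| 10 | 7 | 3 | 4 |

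The gap reaches its maximum of 4 days (days 4 to 7) for events lasting 7 days or more. Measured against no waiting period at all, as in the other five entries, the difference is min(*d*, 7), so up to 7 days.

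**Step 4: is there an earlier Grade 3-4 trigger elsewhere?** None was found in the document. Table 2 covers only holding or stopping pembrolizumab. The other measures in the colitis entry (fluids, monitoring, and consideration of GI consultation and endoscopy from Grade 2) set no steroid start. Section 5.2.5 permits earlier steroids but does not prompt them.

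**The case against.** The strongest reply is that little harm need follow.

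- **The text is advisory and earlier treatment is allowed.** Section 5.2.5 allows "All treatments that the investigator considers necessary" for the patient's welfare, and its list of prohibited medications exempts steroids given for suspected immune events. The fuller ECI guidance document may already give an earlier start. This stands as a limit on the consequence. It does not make the printed prompt right, because such guidance is there for staff who are unsure.
- **The rest of the response is not delayed.** This is true of fluids, perforation monitoring, GI work-up and the Table 2 action on pembrolizumab. Stopping the drug is still not the same as treating the colitis.
- **Four of the five comparators are silent on timing, and only pneumonitis says to start at once.** This is also true. Colitis is moreover the only entry with a persistence condition at Grade 2, which could reflect the need to rule out infection first. That could justify some wait, but not a longer one at the higher grade. The finding rests on the ordering of the two waits, and the comparators only support it.
- **The one-week line might be an escalation step for events already on oral steroids.** The treatments do differ: oral at Grade 2, IV followed by high-dose oral at Grade 3-4. But the Grade 2 line is confined to Grade 2, and nothing says that a Grade 3-4 event should first receive oral steroids.
- **The arithmetic assumes constant grade.** An event that spends more than 3 days at Grade 2 and then worsens has already had an oral-steroid prompt, so its gap for any steroid is zero. This stands, and it narrows the set of events affected.

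**Conclusion.** The concern holds: the Grade 3-4 colitis trigger is wrong as written and should be fixed. The prompt is 0 to 4 days later than the Grade 2 line would give. This applies only to Grade 3-4 diarrhea/colitis that is judged pembrolizumab-related, has not already been prompted while at Grade 2, and has not been treated earlier at the investigator's discretion.

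Confidence in the reading of the text is high. The practical consequence is less certain, because the ECI guidance document was not available and no event rate is given from which to count affected patients. The error is one of safety wording in supportive-care guidance.

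**What to change.** Delete the one-week persistence condition from the Grade 3 or 4 line, so that it directs IV steroids followed by high-dose oral steroids without a waiting period, in line with the other five Grade 3-4 entries. Whether to drop the wait entirely is a clinical decision. If the medical lead wants to keep a persistence condition, it should be no longer than the Grade 2 one (more than 3 days), which is the least that removes the inversion.

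In either case the medical lead should confirm that the corrected line agrees with the ECI guidance document, and the three sites should be notified. The cost is one phrase in the next amendment, one document check and one site notice.

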# • Hypophysitis:

- For Grade 2 events, treat with corticosteroids. When symptoms improve to Grade 1 or less, steroid taper should be started and continued over no less than 4 weeks. Replacement of appropriate hormones may be required as the steroid dose is tapered.
- For **Grade 3-4** events, treat with an initial dose of IV corticosteroids followed by oral corticosteroids. When symptoms improve to Grade 1 or less, steroid taper should be started and continued over no less than 4 weeks. Replacement of appropriate hormones may be required as the steroid dose is tapered.

#### • Hyperthyroidism or Hypothyroidism:

Thyroid disorders can occur at any time during treatment. Monitor patients for changes in thyroid function (at the start of treatment, periodically during treatment, and as indicated based on clinical evaluation) and for clinical signs and symptoms of thyroid disorders.

- Grade 2 hyperthyroidism events (and Grade 2-4 hypothyroidism):
  - In hyperthyroidism, non-selective beta-blockers (e.g. propranolol) are suggested as initial therapy.
  - In hypothyroidism, thyroid hormone replacement therapy, with levothyroxine or liothyroinine, is indicated per standard of care.
- Grade 3-4 hyperthyroidism
  - Treat with an initial dose of IV corticosteroid followed by oral corticosteroids. When symptoms improve to Grade 1 or less, steroid taper should be started and continued over no less than 4 weeks. Replacement of appropriate hormones may be required as the steroid dose is tapered.
- Hepatic:
  - For **Grade 2** events, monitor liver function tests more frequently until returned to baseline values (consider weekly).
    - Treat with IV or oral corticosteroids
  - For Grade 3-4 events, treat with intravenous corticosteroids for 24 to 48 hours.
  - When symptoms improve to Grade 1 or less, a steroid taper should be started and continued over no less than 4 weeks.

#### • Renal Failure or Nephritis:

- For Grade 2 events, treat with corticosteroids.
- For Grade 3-4 events, treat with systemic corticosteroids.
- When symptoms improve to Grade 1 or less, steroid taper should be started and continued over no less than 4 weeks.
- **Management of Infusion Reactions**: Signs and symptoms usually develop during or shortly after drug infusion and generally resolve completely within 24 hours of completion of infusion.

Table 3 below shows treatment guidelines for subjects who experience an infusion reaction associated with administration of pembrolizumab.

#### **NCI CTCAE Grade** Treatment **Premedication at** subsequent dosing Increase monitoring of vital None Grade 1 signs as medically indicated until Mild reaction; infusion the subject is deemed medically interruption not stable in the opinion of the indicated: intervention investigator. not indicated Grade 2 **Stop Infusion and monitor** Subject may be symptoms. premedicated 1.5h ( $\pm$ **Requires** infusion 30 minutes) prior to interruption but responds Additional appropriate medical infusion of promptly to symptomatic therapy may include but is not pembrolizumab (MKlimited to: treatment (e.g., 3475) with: antihistamines, NSAIDS, IV fluids narcotics, IV fluids); prophylactic medications Antihistamines Diphenhydramine 50 indicated for $\leq =24$ hrs mg po (or equivalent NSAIDS dose of antihistamine). Acetaminophen Narcotics Acetaminophen 500-Increase monitoring of vital 1000 mg po (or signs as medically indicated until equivalent dose of the subject is deemed medically antipyretic). stable in the opinion of the investigator. If symptoms resolve within one hour of stopping drug infusion, the infusion may be restarted at 50% of the original infusion rate (e.g., from 100 mL/hr to 50 mL/hr). Otherwise dosing will be held until symptoms resolve and the subject should be premedicated for the next scheduled dose. Subjects who develop Grade 2 toxicity despite adequate premedication should be

permanently discontinued

#### **Table 3 Infusion Reaction Treatment Guidelines**

# Page 45 V8.0

NCI CTCAE Grade	Treatment	Premedication at subsequent dosing
	from further trial treatment administration.	
Grades 3 or 4	Stop Infusion.	No subsequent dosing
Grade 3: Prolonged (i.e., not rapidly responsive to	Additional appropriate medical therapy may include but is not limited to:	
symptomatic medication	IV fluids	
and/or brief interruption of infusion); recurrence	Antihistamines	
of symptoms following	NSAIDS	
initial improvement; hospitalization indicated	Acetaminophen	
for other clinical sequelae	Narcotics	
(e.g., renal impairment, pulmonary infiltrates)	Oxygen	
Grade 4:	Pressors	
Life-threatening; pressor	Corticosteroids	
or ventilatory support indicated	Epinephrine	
multated	Increase monitoring of vital signs as medically indicated until the subject is deemed medically stable in the opinion of the investigator.	
	Hospitalization may be indicated.	
	Subject is permanently discontinued from further trial treatment administration.	

readily available during the period of drug administration.

# **6 STUDY PROCEDURES**

Study procedures should be completed as outlined in the Schedule of Events. Section 6.1 summarizes the trial procedures to be performed at each visit. Individual trial procedures are described in detail below.

# 6.1 Schedule of Events

	Screeni	ng Phase						Тı	reatmen	t Phase					
Treatment Encounter	Part 1	Part 2	Baseline	1	2	3	4	5	6	7	8	9	10	11	12
Scheduling Window	(-28 to -1)	(-14 to -1)	Day 0 e	Day 1	Day 4	Day 11-14	Day 15	Day 25	Day 29	Day 39-42	Day 43	Day 46	Week 9	Week 10 onwards g	End of Study h
Informed Consent	Х														
Inclusion/Exclusion Criteria	Х														
Demographics and Medical History	Х														
Concomitant Medication Review	Х		Х		Х	Х		Х		Х				Xg	Х
Physical Examination		Х	Х			Х		Х		Х				Xg	Х
Vital Signs and Weight		Х	Х			Х		Х		Х				Xg	Х
ECOG Performance Status		Х	Х			Х		Х		Х				Xg	Х
Pregnancy Test – Urine or Serum β- HCG		X m													
PT/INR and aPTT		Х						Х							
CBC & Serum Chemistry a		Х	Xk			Х		Х		Х				Xg	Х
Urinalysis, T3, FT4 and TSH		Х								Х				Xf	Х
ECG		Xi		0				As c	linically	indicated	1				
Tumor Imaging - CT preferred b	Х												Xb		Х
Tissue Biopsy j	X			Х			Х		X		Х				
Correlative Blood Collection c		X						Х				Xc			Х
OBP-301 l,n				Х			Х		Х		Х				
Pembrolizumab Administration d, o					Х			Х				Х		X d	
Review Adverse Events					Х	Х		Х		Х		Х		Xg	Х

- a. Serum chemistry includes sodium, potassium, chloride, bicarbonate, blood urea nitrogen, creatinine, glucose, AST, ALT, Alk Phos, lactate dehydrogenase, bilirubin (total and direct), total protein, albumin, calcium, magnesium and phosphorous, may be drawn up to -2 days from schedule. b. Tumor imaging studies preferably CT scans of chest/abdomen/pelvis should be performed every three cycles of Pembrolizumab after week 10 until end of study.
- c. Correlative blood collection will be done at screening, day 25, day 46, at week 19 and at the end of study. Correlative blood draws will be done predose if treatment is given on the same day.
- d. Pembrolizumab will be administered every 3 weeks  $\pm$  3 days.
- e. Baseline assessment should be performed within 5 days of administrating first dose of OBP-301.
- f. Urinalysis, T3, FT4 and TSH should be performed every 3rd cycle of Pembrolizumab thereafter until end of study.
- g. From week 10 and onwards, concomitant medication review, physical exam, vitals/weight, ECOG performance status, CBC, comprehensive serum chemistry and review of adverse events should be performed every 3 weeks until end of study.
- h. End of study will occur 28 days (+/- 5 days) following study removal, disease progression, or following 2 years on treatment. Patients may still be followed for survival for up to 96 weeks from study start.
- i 12-lead ECG will be recorded after the patient has rested for 5 minutes
- j. Tumor biopsy may be needed during screening phase for PD-L1 testing if there is no archival tissue available.
- k. Only needed, if screening CBC and chemistry done more than 7 days prior to first cycle of pembrolizumab.
- 1. OBP-301 will be administered every 2 weeks (-2 business day/+5 business day window). If the window is used, the following doses should be
- administered following the same window, ensuring at least 12 days between each OBP-301 administration.
- m. Pregnancy test for screening should be done within 7 days of Day 1.
- n. A CBC and CMP should be obtained within 10 days of OBP injection, if not already performed.
- o. OBP-301 and Pembrolizumab should not be administered on the same day.

